**Table 4. Summary of Efficacy Variables and Corresponding Analyses for Efficacy Analysis by Week 12 (Continued)**

Efficacy Variables	Analysis Method
Key Secondary Variables (Continued)	
Continuous Endpoints: 
 
• Change from baseline in DAS28(CRP) at Week 12
 
• Change from baseline in HAQ-DI at Week 12
 
	
 
• LS mean, and 95% CI within each treatment group and LS mean, 95% CI and p-values between each Upadacitinib dose group and the combined placebo group using ANCOVA model with treatment, prior bDMARD use and baseline value as covariates. Both nominal p-value and adjusted p-value through the graphical multiplicity procedure described in Section 9.2.5 will be provided.
 
• Imputation: MI
 
• Analysis Set: FAS
 

Change from baseline in SF-36 Physical Component Score (PCS) at Week 12	
 
• LS mean and 95% CI within each treatment group and LS mean, 95% CI and p-values between each Upadacitinib dose group and the combined placebo group using MMRM model with fixed effects of treatment, visit and treatment-by-visit interaction, prior bDMARD use and baseline value as covariate. Both nominal p-value and adjusted p-value through the graphical multiplicity procedure described in Section 9.2.5 will be provided.
 
• Analysis Set: FAS
 

Additional Variables (summarized at all visits up to Week 12)	
Binary Endpoints: 
 
• ACR20/50/70
 
• LDA and CR based on DAS28(CRP), DAS28 (ESR), SDAI, and CDAI criteria
 
• Proportion of subjects achieving MCID in change from baseline in HAQ-DI among those with baseline HAQ-DI <math>\geq 0.3</math>;
 
• ACR/EULAR Boolean remission;
 
	
 
• Point estimate and 95% CI of the response rate for each treatment group. The 95% CI will be based on normal approximation.
 
• Point estimate, 95% CI and p-value for the treatment comparison between each Upadacitinib dose group and the combined placebo group using the Cochran-Mantel-Haenszel test adjusting for stratification factor prior bDMARD use. Only nominal p-value will be provided, and the 95% CI will be based on normal approximation.
 
• Imputation: NRI for primary analysis and OC for sensitivity analysis
 
• Analysis Set: FAS
 

**Table 4. Summary of Efficacy Variables and Corresponding Analyses for Efficacy Analysis by Week 12 (Continued)**

Efficacy Variables	Analysis Method
Additional Variables (summarized at all visits up to Week 12) (Continued)	
Continuous Endpoints: 
 
• Change from baseline in individual ACR components
 
• Change from baseline in DAS28 (CRP) and DAS28 (ESR)
 
• Change from baseline in CDAI and SDAI
 
• Change from baseline in morning stiffness (severity and duration)
 
• Change from baseline in EQ-5D-5L
 
• Change from baseline in ISI (sleep)
 
• Change from baseline in SF-36
 
	
 
• LS mean and 95% CI within each treatment group and LS mean, 95% CI and p-values between each Upadacitinib dose group and the combined placebo group using MMRM model with fixed effects of treatment, visit and treatment-by-visit interaction, prior bDMARD use and baseline value as covariate. Only nominal p-value will be provided.
 
• Analysis Set: FAS
 

- a. US/FDA regulatory purposes.  
 b. EU/EMA regulatory purposes.

### 9.3 Long-Term Efficacy Analysis

Assessments to evaluate long-term efficacy will be analyzed for the following measures at Week 1, 2, 4, 8, 12, 24, 36, 48, every 12 weeks through Week 240, and at Week 260.

- ACR20/50/70 response rates;
- Change from baseline in individual ACR components;
- Change from baseline in DAS28 (CRP);
- Change from baseline in DAS28 (ESR);
- Change from baseline in CDAI;
- Change from baseline in SDAI;
- Change from baseline in morning stiffness (severity and duration);
- Proportion of subjects achieving LDA and proportion of subjects achieving CR based on DAS28 (CRP), DAS28 (ESR), SDAI, and CDAI criteria;
- Proportion of subjects achieving MCID in change from baseline in HAQ-DI (defined as change from baseline in HAQ-DI  $\leq -0.3$ );

- ACR/EULAR Boolean remission;
- Proportion of subjects with no concomitant corticosteroid use (among subjects with corticosteroid use at baseline).

Assessments to evaluate long-term efficacy will be analyzed for the following measures at Week 4, 12, 24, 48:

- Change from baseline in EQ-5D-5L;
- Change from baseline in ISI (sleep);
- Change from baseline in SF-36.

Analyses will be based on As Observed (AO) data. Descriptive statistics will be provided for each randomized treatment group sequence as defined in Section 9.1.1. These include the number of observations, mean, standard deviation, and 95% CI for continuous endpoints; and frequencies and percentages with 95% CI using normal approximation for binary endpoints. In addition, longitudinal analysis will be performed using MMRM or GLMM as described in Section 9.1.2 for all endpoints except proportion of subjects with no concomitant corticosteroid use. Point estimates and 95% CI from the model will be provided for each treatment group sequence. Plot for each randomized treatment group sequence over time will be provided.

For the purpose of Period 1 CSR, response rate and 95% CI using NRI for binary endpoints will be provided for each randomized treatment group sequence by visits up to Week 24. For continuous endpoints, the LS mean and 95% CI based on MMRM will be reported for each randomized treatment group sequence by visits up to Week 24.

Table 5 below provides the overview of the long-term efficacy analyses to be performed on different endpoints.

**Table 5. Summary of Efficacy Variables and Corresponding Analyses for Long-Term Efficacy Analysis**

Efficacy Variables	Analysis Method
Binary Endpoints:	

 
• ACR20/50/70 response by visit
 
• LDA and CR based on DAS28(CRP), DAS28 (ESR), SDAI, and CDAI criteria by visit
 
• Proportion of subjects with change from baseline in HAQ-DI <math>\leq -0.3</math> and <math>\leq -0.22</math>, respectively
 
• Boolean remission
 
• Proportion of subjects with no concomitant corticosteroid use (among subjects with corticosteroid use at baseline)*
 
	
 
• Point estimate and 95% CI of the response rate for each randomized treatment group sequence
 
• Point estimate and 95% CI of the response rate using GLMM model for each randomized treatment group sequence (*endpoint excluded from this analysis)
 
• Plot for each randomized treatment group sequence over time for key endpoints#
 
• Imputation: AO
 
• Analysis Set: FAS
 

Continuous Endpoints:	

 
• Change from baseline in individual ACR components by visit
 
• Change from baseline in DAS28 (CRP) and DAS28(ESR) by visit
 
• Change from baseline in CDAI and SDAI by visit
 
• Change from baseline in morning stiffness (severity and duration) by visit
 
• Change from baseline in EQ-5D-5L by visit
 
• Change from baseline in ISI (sleep) by visit
 
• Change from baseline in SF-36 by visit
 
	
 
• Point estimate, and 95% CI of mean change from baseline together with SD for each randomized treatment group sequence
 
• Point estimate and 95% CI of change from baseline using MMRM model for each randomized treatment group sequence
 
• Plot for each randomized treatment group sequence over time for key endpoints#
 
• Imputation: AO Analysis Set: FAS
 

# Key endpoints for figures include: ACR20/50/70, LDA and CR based on DAS28(CRP) and CDAI criteria, Boolean remission, change from baseline in DAS28(CRP) and CDAI.

Note: NRI for binary endpoints and MMRM for continuous endpoints were used for analysis up to Week 24, as described in this section. The analyses had been completed prior to SAP Version 3.0 and is no longer mentioned in [Table 5](#) for streamlined summary of future long-term efficacy analysis.

## 9.4 Efficacy Variables Definitions and Conventions

### 9.4.1 ACR Criteria

ACR criteria are a commonly used standard criteria set mentioned in the guidance of American College of Rheumatology to evaluate the effectiveness of investigation drug in

RA clinical trials. It is a composite measurement calculated based on the improvement over a set of core measurements.

ACR20 is defined as at least 20% improvement (compared to baseline values) in tender and swollen joint counts and at least 20% improvement in 3 of the remaining 5 core set measures (subject global assessment of pain, subject global assessment of disease activity, physician global assessment of disease activity, subject assessment of physical function and acute phase reactant hsCRP).

ACR50 and ACR70 are similarly defined with at least 50% and 70% improvement, respectively.

A subject will be classified as an ACR20 (ACR50, ACR70) responder, if the following conditions are met:

1.  $\geq 20\%$  (50%, 70%) improvement from baseline in tender joint count (TJC68) and
2.  $\geq 20\%$  (50%, 70%) improvement from baseline in swollen joint count (SJC66) and
3.  $\geq 20\%$  (50%, 70%) improvement from baseline in at least 3 of the following 5:
  - patient's assessment of pain
  - patient's global assessment of disease activity (PGA)
  - physician's global assessment of disease activity (PhGA)
  - patient's self-assessment of physical function (i.e., measured by Health Assessment Questionnaire HAQ-DI score)
  - Acute-phase reactant value CRP

There are seven components to be evaluated to define an ACR response. Missing values for each component can occur due to a missed visit or due to dropout from the study. Depending on the pattern of the missing components, ACR responses may be or may not be determined using observed values only.

To maximize the utilization of observed information at certain visits and be scientifically as robust as possible, the principle to calculate ACR response is to minimize imputation whenever possible. Observed ACR response will be calculated first based on a derived visit window instead of the nominal visit identifier (e.g., Week 6 visit) collected from the CRF.

To calculate observed ACR responses:

- Identify the observed component xx% improvement indicator (0/1/missing), 1 means achieving  $\geq$  xx% improvement from baseline and 0 means  $<$  xx% improvement from baseline (e.g., xx% representing 20%/50%/70%).
- $ACR_{xx} = 0$  if TJC indicator = 0 OR SJC indicator = 0 OR at least 3 out of 5 components improvement indicators = 0.
- $ACR_{xx} = 1$  if TJC indicator = 1 AND SJC indicator = 1 AND at least 3 out of 5 components improvement indicators = 1.
- For all other cases,  $ACR_{xx} =$  missing since  $ACR_{xx}$  cannot be determined.

The following table illustrates examples for ACR calculations.

Example	TJC 68	SJC 66	Component 1	Component 2	Component 3	Component 4	Component 5	ACR20-Response?
A	1	1	1	1	1	.	.	Yes
B	1	0	1	1	1	1	1	No
C	.	0	.	.	.	.	.	No
D	1	.	1	1	1	1	1	.
E	1	1	0	0	0	1	1	No
F	.	.	0	0	0	.	.	No
G	1	1	1	1	0	0	.	.

Legend: 1 =  $\geq$  20% improved compared to baseline; 0 =  $<$  20% improved compared to baseline; "." Missing

Windowing Rule for ACR Response Calculation:

- ACR component values will first be determined at each date within a visit window.

- ACR component values at each date will be combined to determine the observed ACR composite score at each date in each window.
- After this calculation, if multiple non-missing ACR composite scores are available within a given visit window, the non-missing ACR composite score closest to the target day will be used. If two composite scores have the same distance from the target day, the later one will be used. The corresponding date will be used as the observed ACR response date in the derived efficacy dataset.
- If a non-missing ACR composite score is not available for any day within a given visit window, the windowed component values for that visit will be used to calculate the ACR composite score for that visit window (component value windowing follow the same rules as in steps described above). The date of observed ACR composite score will be determined by the first available ACR component date, in the order of TJC, SJC, Pain, PGA, PhGA, HAQ-DI, CRP/ESR, in the derived efficacy dataset.

When observed ACR xx response for a given visit is missing, imputation methods will be used to calculate "imputed" ACRxx response.

- Non-Responder Imputation (NRI) for ACR response:
  - Step 1: all missing components will be imputed using LOCF, and then the ACR composite score can be calculated.
  - Step 2: if the ACR composite score cannot be determined by step 1, the ACR composite score will be imputed as 0. In addition, subjects who prematurely discontinue from the study drug will be considered as non-responders (ACR = 0) for all subsequent visits after the discontinuation date.

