#### **9.1.2 Definition of Missing Data Imputation**

##### **Non-Responder Imputation (NRI) Approach**

The NRI approach will categorize any subject who has a missing value for categorical variables at a specific visit as non-responder for that visit. In addition, subjects who prematurely discontinue from study drug will be considered as non-responders for all subsequent visits after discontinuation.

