### **Observed Cases (OC)**

The OC analysis will not impute values for missing evaluations. In addition, the OC will not use values after premature discontinuation of study drug. This sensitivity analysis will only be applied to the analysis prior to treatment switching.

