## **9.2 Efficacy Analysis by Week 12**

### **9.2.1 Primary Efficacy Analysis**

The primary endpoint for US/FDA regulatory purposes is ACR20 response at Week 12. The primary endpoint for EU/EMA regulatory purposes is LDA (based on DAS28 (CRP)  $\leq 3.2$ ) at Week 12. Analyses will be conducted separately for US/FDA regulatory purposes and EU/EMA regulatory purposes; for each set of analysis, only one primary endpoint is specified.

Analysis of the primary endpoint will be conducted on the FAS based on randomized treatment groups (Upadacitinib 15 mg QD, Upadacitinib 30 mg QD and the combined placebo groups). Point estimate and 95% CI using normal approximation will be

provided for the response rate for each randomized treatment group. Comparisons of the primary endpoint will be made between each Upadacitinib dose and the combined placebo group using the Cochran-Mantel-Haenszel test adjusting for stratification factor prior bMDARD use. Point estimate, 95% CI using normal approximation and p-value for the treatment comparison will be presented. Both the nominal p-value constructed using the Cochran-Mantel-Haenszel test and the adjusted p-value through the graphical multiplicity procedure described in Section 9.2.5 will be provided. For the primary analysis, non-responder imputation (NRI) will be used.

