**Table 4. Summary of Efficacy Variables and Corresponding Analyses for Efficacy Analysis by Week 12**

Efficacy Variables	Analysis Method
Primary Variables	

 
• ACR20 response at Week 12a
 
• LDA as measured by DAS28(CRP) at Week 12b
 
	
 
• Point estimate and 95% CI of the response rate for each Upadacitinib dose group and the combined placebo group. The 95% CI will be based on normal approximation.
 
• Point estimate, 95% CI and p-value for the treatment comparison between each Upadacitinib dose group and the combined placebo group, where the p-value is constructed using the Cochran-Mantel-Haenszel test adjusting for stratification factor prior bDMARD use. Both nominal p-value and adjusted p-value through the graphical multiplicity procedure described in Section 9.2.5 will be provided. The 95% CI will be based on normal approximation.
 
• Subgroup analysis.
 
• Imputation: NRI for primary analysis and OC for sensitivity analysis
 
• Analysis Set: FAS and Per Protocol Analysis Set as supportive analysis (NRI only).
 

Key Secondary Variables	

Binary Endpoints:
 
 
• ACR50/70 response at Week 12
 
• ACR20 response at Week 12b
 
• LDA as measured by DAS28(CRP) at Week 12a
 
• ACR20 response at Week 1
 
	
 
• Point estimate and 95% CI of the response rate for each treatment group. The 95% CI will be based on normal approximation.
 
• Point estimate, 95% CI and p-value for the treatment comparison between each Upadacitinib dose group and the combined placebo group using the Cochran-Mantel-Haenszel test adjusting for stratification factor prior bDMARD use. For ranked key secondary endpoints, both nominal p-value and adjusted p-value through the graphical multiplicity procedure described in Section 9.2.5 will be provided. The 95% CI will be based on normal approximation.
 
• Imputation: NRI for primary analysis and OC for sensitivity analysis
 
• Analysis Set: FAS
 

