**Table 6. Anatomical Joints Assessed for Calculation of Tender and Swollen Joint Counts (TJC68 and SJC66)**

Temporomandibular	Sternoclavicular	Acromio-clavicular	Shoulder
Elbow	Wrist	Metacarpophalangeal I	Metacarpophalangeal II
Metacarpophalangeal III	Metacarpophalangeal IV	Metacarpophalangeal V	Thumb Interphalangeal
Proximal Interphalangeal II	Proximal Interphalangeal III	Proximal Interphalangeal IV	Proximal Interphalangeal V
Distal Interphalangeal II	Distal Interphalangeal III	Distal Interphalangeal IV	Distal Interphalangeal V
Hip a	Knee	Ankle	Tarsus
Metatarsophalangeal I	Metatarsophalangeal II	Metatarsophalangeal III	Metatarsophalangeal IV
Metatarsophalangeal V	Great Toe/Hallux	Interphalangeal II	Interphalangeal III
Interphalangeal IV	Interphalangeal V		

a. Hip joints are not assessed for swelling.

At each study visit, a joint evaluator assessed whether a particular joint was "tender or painful" where presence of tenderness was scored as "1" and the absence of tenderness was scored as "0," provided the joint was not replaced ("9") or could not be assessed ("NA") due to other reasons (e.g., post-corticosteroid joint injection). The total tender joint count (TJC68), which is based on 68 joints, will be derived as the sum of all "1s" and proportional extrapolation will be used to impute joint counts for the joints that are replaced or not assessed. A similar method will be followed for the derivation of total swollen joint count (SJC66), which is based on 66 joints as the hip joints are excluded. Thus, the range for TJC68 will be 0 to 68 and 0 to 66 for SJC66.

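### Does the SAP leave it open whether a missing Week 12 ACR response is scored as non-response outright or only after carrying components forward?

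*SAP*

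**What the plan says.** SAP 9.1.2 gives the general rule: "The NRI approach will categorize any subject who has a missing value for categorical variables at a specific visit as non-responder for that visit". It adds that subjects who stop study drug early are non-responders at later visits. It mentions neither ACR nor carry-forward.

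SAP 9.4.1 has its own NRI rule for ACR response, triggered when the observed ACR response at a visit is missing. It opens with "Step 1: all missing components will be imputed using LOCF, and then the ACR composite score can be calculated" and continues with "Step 2: if the ACR composite score cannot be determined by step 1, the ACR composite score will be imputed as 0". It then repeats the discontinuation rule of 9.1.2.

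The sections that call on the method do not say which text they mean. SAP 9.2.1 has "For the primary analysis, non-responder imputation (NRI) will be used". Table 4, for the primary and the binary key secondary endpoints, has "Imputation: NRI for primary analysis and OC for sensitivity analysis". The protocol's definition of NRI (8.1.4.1.5) covers only discontinuation of study drug.

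Two other provisions in the SAP reduce how often an ACR response is undetermined. If no single date in a window gives a score, "the windowed component values for that visit will be used to calculate the ACR composite score for that visit window" (9.4.1). For individual joints, "proportional extrapolation will be used to impute joint counts for the joints that are replaced or not assessed" (9.4.2).

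**The concern.** Both rules start from the same event, a missing ACR response at a visit, and for a subject still on drug they can give opposite answers. In the example table of 9.4.1, Example D (swollen joint count missing) and Example G (fifth component missing) are undetermined on observed data. Section 9.1.2 makes both non-responders. Section 9.4.1 makes either a responder if the component carried forward had improved by at least 20%. Even a subject with no Week 12 data at all could count as a Week 12 responder on earlier values.

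ACR20 at Week 12 is the US primary endpoint and a ranked EU secondary, and ACR50 and ACR70 are unranked key secondaries. The planned checks do not seem to help. Observed Cases leaves the affected subjects out, and the Per Protocol analysis uses NRI and so inherits whichever rule was applied. If the text were truly open, an analyst could choose the rule, and a reader could not tell whether the result rested on carried-forward components.

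**Working it through.** **1. Which rule governs.** Section 9.4.1 sits among the endpoint definitions. It names the method (NRI), the endpoint (ACR response) and the trigger (observed response missing). It restates the discontinuation rule of 9.1.2, so it is a complete NRI rule for this endpoint. If 9.1.2 applied to ACR without it, Step 1 would never operate. The only reading that gives effect to both texts is that 9.1.2 is the default and 9.4.1 is its ACR form.

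**2. Where the rules differ.** Subjects off study drug are non-responders under both. Patterns already settled by observed components (Examples A, B, C, E and F) are the same under both. ACR20 at Week 1 is the same, because carrying baseline forward gives 0% improvement. What remains is subjects on drug with an undetermined ACR response after Week 1.

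**3. Whether the strict result can be seen.** For Observed Cases, "The OC analysis will not impute values for missing evaluations", and values after discontinuation of study drug are not used. Observed Cases responders are therefore exactly the observed, on-drug responders, which is the numerator of strict NRI. Hence:

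- strict NRI rate = Observed Cases responders / Full Analysis Set N
- responders owed to carry-forward = NRI responders − Observed Cases responders

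Observed Cases is planned for Week 12 ACR20, ACR50 and ACR70.

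**4. The plan's power figure.** Inputs from SAP 4.3: 27% against 47%, two-sided alpha 0.025, 10% dropout. With 150 per comparison group, n = 150 × 0.9 = 135. A two-proportion normal approximation gives power of 88.3% (pooled variance) or 89.2% (unpooled), consistent with the stated approximately 90%.

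**5. Size of the difference between the rules.** The documents give no rate of undetermined on-drug Week 12 ACR20. Assume a share m in each group, with carried-forward response at the design rates. Then:

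- active subjects changing status = 135 × m × 0.47
- placebo subjects changing status = 135 × m × 0.27
- strict difference = 20 × (1 − m) points

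| m | Undetermined per group | Active changed | Placebo changed | Strict rates | Difference | Power (pooled) |
|---|---|---|---|---|---|---|
| 0 | 0 | 0 | 0 | 47.0% vs 27.0% | 20.0 | 88.3% |
| 1% | 1.35 | 0.63 | 0.36 | 46.5% vs 26.7% | 19.8 | 87.7% |
| 3% | 4.05 | 1.90 | 1.09 | 45.6% vs 26.2% | 19.4 | 86.5% |
| 5% | 6.75 | 3.17 | 1.82 | 44.7% vs 25.7% | 19.0 | 85.3% |

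Step 3 at m = 3% on the active arm: carry-forward responders 135 × 0.47 = 63.45; Observed Cases responders 63.45 − 1.90 = 61.55; 61.55 / 135 = 45.6%, the strict rate in the table.

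If the 10% dropouts stay in the 150 as non-responders, the rates are 0.9 × 47 = 42.3% and 0.9 × 27 = 24.3%, a difference of 18.0 points. Multiplying by (1 − m) gives 17.82 at 1% and 17.10 at 5%, a change of 0.18 to 0.90 points.

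If the share differs by arm, carry-forward minus strict is 0.02 × 47 − 0.04 × 27 = −0.14 points (active 2%, placebo 4%) or 0.04 × 47 − 0.02 × 27 = +1.34 points (active 4%, placebo 2%). The extreme bound is 5% undetermined in one arm only, with every one a carried-forward responder. That moves the difference by 5 points in either direction.

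**The case for a change.** The strongest case is that a primary endpoint should not depend on a reader inferring precedence. Section 9.1.2 states no exception, the analysis sections give no cross-reference, and the protocol's NRI mentions neither carry-forward nor missing data on drug. A method labelled NRI that lets a wholly missed Week 12 visit count as a response is not what most readers expect. The EU primary endpoint has no such step: a missing DAS28 component leaves the score missing (SAP 9.4.6), so 9.1.2 makes it a non-response. The two regions' primary endpoints thus treat missing components differently under one label. No stratified comparison under strict scoring is planned, and with unequal missingness the direction of the effect is not fixed.

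Most of this stands as description. The cross-reference is absent and the label is loose. It does not establish an open choice, because the ACR rule is written out as the NRI rule for ACR. Nor does it establish that the dependence is hidden, since the strict rates and the carry-forward count follow from the NRI and Observed Cases results. That recovery needs the Observed Cases counts to be shown; SAP 9.2.2 promises a point estimate and confidence interval, so it rests on the usual display of numerator and denominator. What cannot be read off is the strict Cochran-Mantel-Haenszel p-value. The 5-point bound needs all the missingness in one arm and every affected subject to be a responder, and nothing in the documents points that way.

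**Conclusion.** The plan can stand. The mismatch is a missing cross-reference that an analyst fills sensibly: the endpoint-specific rule applies to ACR and the general rule to the other binary endpoints. Following the text as written gives one determinate result.

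A separate strict analysis would add little. Under equal shares of 1% to 5%, it moves the planned 20-point difference by 0.2 to 1.0 points. In-window combination of components and joint extrapolation push toward the low end. Both the share and the carried-forward response rates are assumptions.

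An edit now would also govern no remaining analysis. SAP 11.1 limits version 3.0 to future long-term reporting, which uses As Observed data; the NRI analyses to Week 24 were finished before it. The primary analysis ran under version 2.0, which is not available here. The version 3.0 change list shows no edit to 9.4.1 and changes 9.1.2 only for the long-term models, so the wording was probably the same, but that is an inference. A sentence in the study report giving the number of on-drug subjects whose Week 12 ACR20 was set by carried-forward components would be a courtesy to readers. The documents show no threat to the primary conclusion.
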